## **1. Basic information**

### **1.1. Purpose of the study**

- Main objective  
To observe the safety, tolerability and toxicity of Ad-TD-nsIL12 intratumoral injection in pediatric DIPG patients (NCI-CTCAE V5.0).
- Secondary objectives
  - 12-month overall survival (OS12), tumor response, Ad-TD-nsIL12-induced immune response.
  - Change in quality of life over time.
  - Collect tumor and blood samples for molecular and immunological studies.

### **1.2. Foundation Information**

Supported by the National Key Research and Development Program of China (No. 2019YFC1316104): Clinical trials and therapeutic mechanisms of novel oncolytic viruses for tumor therapy.

### **1.3. Study location**

Sanbo Brain Hospital, Capital Medical University, Beijing, China.

### **1.4. Research time**

From January 2023, the estimated research period is 2 years. Enrollment of the first patient is expected to occur on January 4th, 2023.

### **1.5. Study diseases**

Primary Pediatric Diffuse Intrinsic Pontine Glioma (DIPG).

### **1.6. Estimated number of patients**

9-18 people.

## **2. Background and feasibility of the study**

### **2.1. Background**

Diffuse intrinsic pontine glioma (DIPG) is a disease associated with histone mutations and is the leading cause of brain tumor-related death in children. Due to the specificity of the tumor location and the high infiltration, the current treatment options for this disease are very limited. Despite of the short-term benefit of standardized radiotherapy in the treatment of DIPG, the prognosis remains poor, with progressive neurological deterioration and median survival less than 1 year and 2-year survival less than 10%. Due to the severe lack of treatment for DIPG, it is imperative to seek a variety of emerging treatments, including oncolytic viruses.

Over the past 20 years, molecular and genetic tools have been available to build new viruses that transfer exogenous genes into cancer cells. The initial study used viral vectors with replication defects to deliver various genes to target tissues. These gene therapies have also shown efficacy and safety in multiple preclinical tumor animal models. However, these promising preclinical results have not been successfully translated into patient benefit in clinical practice. This defect is largely due to the inability of viral vectors to transform cancer cells in large numbers. Typically, these vectors infect only a small number of cells in the body, and in the best case no more than 15%. With the development of molecular biology and genetic engineering technology, viruses selective replication in tumor cells became possible, leading to tumor infection and continuous tumor destruction. This method was first developed and utilized in herpesviruses. In recent years, many other kinds of oncolytic viruses with selective ability to replicate in tumor have been developed. Adenoviruses (AdV) are particularly well-suited to this approach because they cause the least disease in humans and can be genetically

manipulated to infect and replicate in dividing and non-dividing cells. A variety of highly replicable AdV has been shown to be safe in clinical trials. E1B-55K and E3B gene deletion adenovirus type 5 (Ad5) H101 is the first international oncolytic virus product approved by China in 2005. Similarly, recombinant replicating active AdV, containing multiple gene deletions, has been produced, and their effectiveness as therapeutic agents has been validated in vivo and in vivo models of many primary and metastatic tumors. These animal model-based experiments provide valuable information about the effectiveness and safety of the virus. Experiments have clearly demonstrated that by altering these genes, whether through deletion, insertion, or point mutation in coding regions, the resulting virus will kill dividing tumor cells but is non-toxic after delivery to normal brain tissue.

Therefore, it is possible to develop an ideal, stable genetically engineered virus to selectively kill glioma cells. The brain is an immune "exempt" area, which is also a reason for the poor treatment effect, rapid development and poor prognosis of brain tumors, which is an advantage of oncolytic virus therapy. Therefore, brain tumors are suitable targets for intervention by oncolytic viruses, which use conditionally replicated viruses to replicate in tumors and kill tumor cells while preserving the normal cell population in the brain. In recent years, some clinical trials of oncolytic viruses for the treatment of brain tumors have shown good treatment prospects.

## **2.2. Pre-clinical Research on Ad-TD-nsIL12**

In terms of safety, all preclinical safety studies of Ad-TD-nsIL12 have been completed, and the long-term toxicity tests of golden gopher and cynomolgus monkeys indicate that the safe dose of Ad-TD-nsIL12 is at the level of  $5 \times 10^{11}$  vp, which is significantly higher than the effective dose of tumor lysis in animal tests. In terms of efficacy, completed preclinical pharmacodynamic studies of Ad-TD-nsIL12 have shown that Ad-TD-nsIL12 at  $5 \times 10^9$  vp levels can effectively treat a variety of solid tumor models in nude mice and golden gopher. At the same time, the production process of Ad-TD-nsIL12 is clear and controllable, and the quality of the three batches of pilot continuous production is all qualified and stable.

## **2.3. A study of Ad-TD-nsIL12 in the treatment of recurrent glioblastoma**

Between December 2019 and September 2022, a total of 8 patients were recruited to receive Ad-TD-nsIL12 treatment at the Sanbo Brain Hospital of Capital Medical University. The trial assigned three dose-escalation cohorts ( $5 \times 10^9$ ,  $1 \times 10^{10}$ ,  $5 \times 10^{10}$  vp, 1ml). The most common adverse events were fever and cognitive impairment. Nausea and vomiting also occurred frequently, and the dose used in Cohort 2 ( $1 \times 10^{10}$  vp) was used as the maximum tolerated dose (MTD).

One patient had a complete response after treatment with Ad-TD-nsIL12 and is still alive, while another patient received a partial response. In addition, Ad-TD-nsIL12-related proteins (E1A and hexon) were observed in both post-treatment samples, indicating that Ad-TD-nsIL12 remained active for a longer period of time after surgery. Clearance of the enhancement in the injection area was observed after administration of Ad-TD-nsIL12, and the samples collected also showed higher infiltration of CD3+, CD4+ and CD8+ cells than pre-treatment samples. This is consistent with preclinical studies: the antitumor efficacy of Ad-TD-nsIL12 depends on CD8+ T cells and suggests that Ad-TD-nsIL12 induces a long-term immune response.

# **3. Screening of study patients**

## **3.1. Inclusion criteria**

3.1.1. Informed consent of the parents or patient.

- 3.1.2. Patient must be, in the investigator opinion, able to comply with all the protocol procedures.
- 3.1.3. Age 1-18 years.
- 3.1.4. A negative pregnancy test in fertile women (women are considered of childbearing potential (WOCBP) after menarche, unless permanently infertile, including hysterectomy, bilateral salpingectomy, and bilateral oophorectomy).
- 3.1.5. Patient newly diagnosed of DIPG in MRI.
- 3.1.6. Pre-enrollment patients LPS (patients aged  $\geq 1$  and  $< 16$  years) and KPS (patients aged  $\geq 16$  years)  $\geq 50$ .
- 3.1.7. Lesion considered by the investigator to be accessible for stereotactic biopsy. The location of the lesion allows injection without virus entering the ventricular system.
- 3.1.8. No previous treatment for DIPG.

## **3.2. Exclusion criteria**

- 3.2.1. Serious infections or intercurrent conditions, including but not limited to severe renal failure, liver failure, heart failure, or bone marrow failure, which are not permitted for inclusion according to the investigator's criteria. Patients must be afebrile at baseline ( $< 38^{\circ}\text{C}$ ).
- 3.2.2. Other investigational medications within 30 days prior to viral treatment.
- 3.2.3. Participants with immunodeficiency, autoimmune disease, or active hepatitis.
- 3.2.4. Any medical or psychological condition that might interfere with the patient's ability to participate if older than 16 years or parents ability when younger than 16, or give informed consent or would compromise the patient's ability to tolerate therapy or any disease that will obscure toxicity or dangerously alter drug metabolism.
- 3.2.5. Tumor with multiple location.
- 3.2.6. Pregnant or breast-feeding females.
- 3.2.7. Severe bone marrow hypoplasia.
- 3.2.8. Transaminases (aspartate aminotransferase (AST) and/or alanine aminotransferase (ALT)) or total bilirubin  $> 3$  times the upper limit of normal.
- 3.2.9. Neutrophils  $< 1 \times 10^9/\text{L}$ .
- 3.2.10. Platelets  $\leq 100 \times 10^9/\text{L}$ .
- 3.2.11. Hemoglobin  $< 9$  g/dl.
- 3.2.12. Patients with Li-Fraumini syndrome or a known germline defect in the retinoblastoma gene or its associated pathways.
- 3.2.13. Administer any type of vaccine within 30 days prior to Ad-TD-nsIL12 administration.
- 3.2.14. Blood transfusions or drugs (such as G-CSF) within 28 days before baseline to treat pancytopenia or other blood disorders.

## **4. Study design**

### **4.1. Overall design**

Single-arm, single-center, drug safety assessment clinical trial with a 3+3 dose escalation design.

### **4.2. Screening and Selections**

Patients will be screened at the clinic by the investigators. Screening will be performed within 15 days prior to the use of Ad-TD-nsIL12. Prior to screening, investigators will present parents and patients with complete information about the clinical study and sign an informed consent form. Enrollment to the trial will be possible only if the following screening trials are performed and the inclusion and exclusion criteria are met:

- Physical examination, including vital signs and weight.
- Neurological examination and functional status assessment (including Lansky

Performance Status Score (LPS) for patients aged one to under 16 years of age, and Karnofsky Performance Status (KPS) for patients 16 years of age or older).

- Quality of Life Assessment (PedsQL™).
- Clinical laboratory tests, including hematology, chemistry (containing C-reactive protein), and coagulation.
- Detection of adenovirus antigens and anti-adenovirus antibodies in serum.
- Pregnancy test (serum).
- Serological testing for HIV and HBV/HCV.
- MRI (with or without gadolinium), baseline (completed within 15 days prior to viral treatment).
- Medication.

To reduce losing follow-up, participants will be asked to provide contact details of two or more relatives.

### 4.3. In-hospital period

- After stereotactic biopsy, the Ommaya reservoir will be inserted through the biopsy channel and a single injection of Ad-TD-nsIL12 will be delivered immediately after surgery.
- The injection dose start with  $3 \times 10^9$ vp (D1) and follow  $1 \times 10^{10}$ vp (D2),  $3 \times 10^{10}$ vp (D3) for climbing. If 2 or 3 patients develop severe adverse event (SAE) according to NCI-CTCAE at D1. The dose will then be reduced to  $1 \times 10^9$ vp (D0). If one patient develops SAE at the D1 dose, the other 3 patients will continue to be included with the D1 dose to assess whether the occurrence of this SAE is accidental. If SAE develops in 1 of the next 3 patients, following patients will receive the D0 dose.
- Before subsequent patients enrollment, the former patient in each cohort must be observed for at least 6 days after virus injection. The administration of virus to participants in the new cohort will be at least 10 days behind the last participant in the previous cohort.
- If the patient presents with symptoms of decreased brain function or decreased cardiovascular perfusion, or if there is an allergic reaction or signs of anaphylaxis, administration of Ad-TD-nsIL12 should be discontinued. In addition, treatment of Ad-TD-nsIL12 will also be interrupted if other AEs deemed necessary by investigators to be interrupted. In addition, if ventricular penetration is considered to have occurred during viral use, the dosing procedure will be terminated and no further treatment with Ad-TD-nsIL12 will be given, and such patients will be observed and examined by virologic testing (AdV) and further follow-up.
- The tumor tissue obtained at the time of biopsy or excision, as well as the collected blood samples, will be archived in our hospital for future analysis.
- Visit 0:  $3 \pm 1$  days after Ad-TD-nsIL12 injection. Including:
  - Physical examination, including vital signs, weight, and height;
  - Neurological examination and functional status assessment (LPS or KPS), life quality assessment;
  - Blood tests, blood biochemistry (containing C-reactive protein), coagulation function assessment and other blood tests (including detection of adenovirus antigens and anti-adenovirus antibodies in serum);
  - MRI (with or without gadolinium) and tumor response assessment;
  - Assessment and documentation of adverse events, including concomitant medications, including steroids.
- When the patient is discharged, the patient and his or her relatives will be provided with the investigator's contact information in case of an emergency. In addition,

after discharge, the patient can follow the recommended treatment of his/her pediatric oncologist in other hospitals, and the investigators of the experimental group will contact the hospital for follow-up visits. If the investigators think it is necessary, follow-up could be done at Sanbo Brain Hospital.

- Radiation therapy will start 2-6 weeks after the biopsy and virus injection at the discretion of the radiation therapist.

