#### 4.4. Follow-up period

- After enrollment, clinical follow-up will be conducted every 4 weeks for the first 3 months after viral treatment. After 3 months, follow-up visits can be performed by phone, images and blood tests results can be sent by email, or patients can come to our hospital for treatment and follow-up if they wish. Treatment tolerability was measured by severity classification of adverse events (NCI-CTCAE V5.0) and correlation with the investigating drug.
- Visit 1: 28±5 days after Ad-TD-nsIL12 injection. Including:
  - Physical examination, including vital signs, weight, and height.
  - Neurological examination and functional status assessment (LPS or KPS);
  - Quality of Life Assessment (PedsQL™);
  - Laboratory blood tests, some of which will be retained for subsequent analysis;
  - MRI (with or without gadolinium) and tumor response assessment;
  - Evaluation and documentation of adverse events, concomitant medications;
  - Steroid evaluation.
- Visit 2: 8±1 weeks after Ad-TD-nsIL12 injection. Including:
  - Physical examination, including vital signs, weight, and height.
  - Neurological examination and functional status assessment (LPS or KPS);
  - Quality of Life Assessment (PedsQL™);
  - Laboratory blood tests, some of which will be retained for subsequent analysis;
  - MRI (with or without gadolinium) and tumor response assessment;
  - Evaluation and documentation of adverse events, concomitant medications;
  - Steroid evaluation.
- Visit 3: 12±1 weeks after Ad-TD-nsIL12 injection. Including:
  - Physical examination, including vital signs, weight, and height.
  - Neurological examination and functional status assessment (LPS or KPS);
  - Quality of Life Assessment (PedsQL™);
  - Laboratory blood tests, some of which will be retained for subsequent analysis;
  - MRI (with or without gadolinium) and tumor response assessment;
  - Evaluation and documentation of adverse events, concomitant medications;
  - Steroid evaluation.
- Visit 3 is the last designated clinical follow-up, after which the patient's overall AE will be concluded and assessed.
- Except for the 3 planned visits, both patients and investigators may request unplanned follow-up at any time.
- During follow-up, if viral infection of CSF is suspected, the investigator will decide whether to perform virological (AdV) testing.

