#### **4.8. Dose escalation and determination of the maximum tolerated dose**

**(MTD).**

- The dose will start with  $3 \times 10^9$ vp. Three dose stages are planned:  $3 \times 10^9$ vp,  $1 \times 10^{10}$ vp as well  $3 \times 10^{10}$ vp.
- Each cohort will include 3 to 6 participants depending on the occurrence of AE. The criteria for dose climbing are as follows:
  - If there were no Ad-TD-nsIL12 related SAEs (NCI-CTCAE  $\geq$  grade 3) occurred within 6 days after virus injection in the previous patient in the same cohort, the latter patient continues to be included.
  - If 1 patient developed Ad-TD-nsIL12 related SAE in a cohort, 3 patients will continue to be included in this cohort to verify whether it's accidental, and if any 1 of the subsequent 3 patients developed Ad-TD-nsIL12 related SAE, it would be considered as the dose limiting toxicity (DLT), and the previous dose is taken as the maximum tolerated dose (MTD).
  - If 2 patients in the same cohort developed investigational drug-related SAE, it will be considered to be DLT, then the trial will be terminated and the dose used in previous cohort will be defined as MTD.
  - If all 3 patients in the same cohort had no drug-related SAE within 10 days after virus injection, the dose would be upgraded to the next cohort.
  - If DLT presented in the first cohort (D1), dose adjustment will be made according to what is described in protocol 4.3, and if DLT still occurs at D0, the trial terminates.
  - If DLT still does not occur at the highest dose D3, MTD is not defined and the trial terminates.
- Any clinical SAEs deemed to be likely to be associated with Ad-TD-nsIL12 will be recorded by the investigator and graded accordingly. Follow-up will continue until the SAE disappears or drops to grade 1.
- In addition, if non-neurological complications related to any surgical or anesthesia management occur (including, but not limited to, respiratory failure, pneumonia and other systemic infections, cardiac arrest, myocardial infarction, pulmonary embolism, deep vein thrombosis, tracheal and laryngeal trauma, postanesthesia lethargy, fatigue, and short-term memory loss), dose reduction may be considered after discussion with the principal investigator.

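### Section 4.3's rule for leaving D1 does not require the event to be related to the virus, as 4.8 does, and 8.1's safety-committee trigger stops at grade 4

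*Protocol*

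**What the plan says.** **Section 4.3** has three triggers at the starting dose D1, none of which mentions relatedness:

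- Direct step to D0: "If 2 or 3 patients develop severe adverse event (SAE) according to NCI-CTCAE at D1".
- Expansion: "If one patient develops SAE at the D1 dose, the other 3 patients will continue to be included with the D1 dose".
- D0 after expansion: "If SAE develops in 1 of the next 3 patients, following patients will receive the D0 dose".

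**Section 4.8** sets the dose-escalation rule for every cohort. Its first criterion fixes the event as related to Ad-TD-nsIL12 and of CTCAE grade 3 or higher, and the bullets that follow keep the relatedness condition:

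- Expansion: "If 1 patient developed Ad-TD-nsIL12 related SAE in a cohort, 3 patients will continue to be included in this cohort".
- DLT: "If 2 patients in the same cohort developed investigational drug-related SAE, it will be considered to be DLT".
- Escalation: "If all 3 patients in the same cohort had no drug-related SAE within 10 days after virus injection, the dose would be upgraded".

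Section 4.8 adds that a DLT in the first cohort is handled by the dose adjustment in 4.3. Its last bullet lets the team consider a dose reduction, after discussion with the principal investigator, for non-neurological surgical or anesthesia complications.

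**Section 8.4** treats only association levels 4 and 5 as related, so an event rated unrelated, unlikely or possible does not count under 4.8.

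**Section 8.1** has the safety committee evaluate an SAE that the investigator judges dose-related, with the grade given as 3 to 4. The committee may then change or stop recruitment. Section 8.3 lists fatal events first among SAEs. Section 8.6 requires a related death to be reported to the sponsor within 24 hours and does not mention the committee.

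**The concern.** The MTD is the primary endpoint, and 10.1 defines it from the dose that causes DLT. The rule for leaving D1 should therefore have one reading, yet 4.3 and 4.8 state it with different events.

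The difference would arise in a foreseeable setting. Virus is given immediately after stereotactic biopsy and Ommaya insertion (4.3), and 7.3 lists hemorrhage, focal neurological deficit, coma and death among the biopsy risks. A severe event soon after injection may well come from the procedure. An investigator who follows 4.3 to the letter could abandon the starting dose for events that 4.8 does not count as DLT.

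The 8.1 point is separate. The committee trigger names grades 3 and 4, so a related death, the gravest outcome, is the one it does not literally cover.

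**Working it through.** **Planned size.** Three cohorts of 3 to 6 (4.8, 10.2) give 3 × 3 = 9 and 3 × 6 = 18, which matches the 9-18 in 1.6. The wording at issue does not enter that figure.

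**Inputs.** For the first three D1 patients, let R be the number with a related severe event (8.4 level 4 or 5, grade 3 or higher) and U the number whose only severe events are not so rated. Section 4.8 counts R. Section 4.3, read literally, counts R + U. The steps are: 0 → D2; 1 → expand D1; 2 or 3 → D0 (under 4.8, a D1 DLT reaches D0 through its reference to 4.3).

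**All splits with R + U ≤ 3** (4 + 3 + 2 + 1 = 10):

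| R | U | 4.3 literal (R + U) | 4.8 (R) | Same? |
|---|---|---|---|---|
| 0 | 0 | D2 | D2 | yes |
| 0 | 1 | expand | D2 | no |
| 0 | 2 | D0 | D2 | no |
| 0 | 3 | D0 | D2 | no |
| 1 | 0 | expand | expand | yes |
| 1 | 1 | D0 | expand | no |
| 1 | 2 | D0 | expand | no |
| 2 | 0 | D0 | D0 | yes |
| 2 | 1 | D0 | D0 | yes |
| 3 | 0 | D0 | D0 | yes |

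The step differs in 5 of 10 splits. In 2 of them, (0,2) and (0,3), one section gives D0 and the other D2. In all five, 4.3 gives the more cautious step. The 4.8 column shows the automatic rule only. Where the unrelated events are non-neurological surgical or anesthesia complications, 4.8's last bullet already allows a reduction by discretion. The clean example is therefore a neurological deficit from the biopsy.

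**After expansion.** With one related event in the first three, both sections add three patients. One unrelated severe event among those three meets 4.3's trigger for D0, but under 4.8 the cohort still has only one related event and no DLT.

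**Timing.** Section 4.3 says "The administration of virus to participants in the new cohort will be at least 10 days behind the last participant in the previous cohort", and 4.8 escalates on 10 clear days. Both use 6 days between patients within a cohort. There is no conflict here.

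**With the 4.8 event written into 4.3**, both columns count R and all 10 splits agree.

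**Grade 5.** Section 4.8 (grade 3 or higher) includes death, 8.3 includes death, and 8.6 sends a related death to the sponsor. Only 8.1 stops at grade 4, and no other section sends the event to the committee.

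**The case against.** The strongest reply is that 4.3 is not a rival rule. Section 4.8 is the dose-escalation section. It is the only place where DLT is defined, and it calls on 4.3 only once a D1 DLT has occurred. Both sections give the same reason for expanding, namely to see whether the event was accidental. Section 4.4 measures tolerability by "severity classification of adverse events (NCI-CTCAE V5.0) and correlation with the investigating drug", and 10.1 speaks of the dose that causes DLT. On that reading 4.3 inherits the related-only event and nothing conflicts. This stands as the likely intent. It does not settle the text, because 4.3 states its own event and its own counts and does not limit itself to DLT.

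It is also fair that the literal reading never gives a child a higher dose than 4.8 allows, and that non-neurological procedural complications have their own discretionary provision in 4.8. Both limit the size of the point.

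A reader might infer from 5 of 10 that the sections would disagree in about half of trials. The documents do not support that. The 10 splits are not equally likely, three of the five differences involve expansion rather than D0 against D2, and the protocol gives no rate for related or unrelated severe events.

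On 8.1, nothing bars the committee from reviewing a death, and 9.5 allows early termination for serious unforeseen risks. A reader might infer that a related death would go uncounted or unreported. It would not, given 4.8 and 8.6. Only the committee trigger has the gap.

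**Conclusion.** The point holds as a wording conflict in a rule that feeds the primary endpoint. Read literally, two or three unrelated severe events among the first three D1 patients satisfy 4.3's condition for D0 and 4.8's condition for D2. The effect is confined to D1 and the step to D0, and it errs towards caution. It disappears if 4.3 is read as related-only, which is probably what was meant. The comparison of rules assumes no event rates, and no probability is claimed.

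It would go too far to say that the escalation design is unsound, that the MTD is undefined because of this, or that the observation windows clash. The documents support none of these.

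The 8.1 omission is a second, smaller slip: a related grade 5 event falls outside the stated committee trigger while being covered elsewhere for dosing and sponsor reporting.

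**What to change.** - **4.3:** in the D1/D0 rule, replace the severe-adverse-event wording in "If 2 or 3 patients develop severe adverse event (SAE) according to NCI-CTCAE at D1", and each later SAE in that rule, with: Ad-TD-nsIL12-related (8.4 level 4 or 5) adverse event of CTCAE v5.0 grade 3 or higher.
- **4.8:** leave the discretionary bullet on surgical and anesthesia complications and the 6-day and 10-day timing as they are.
- **8.1:** change the committee trigger from a dose-related SAE of grade 3 to 4 to an Ad-TD-nsIL12-related SAE of grade 3 or higher, including death. This also corrects dose-related, which does not match the drug-related term in 4.8.

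The cost is a wording amendment to two sections, with the sponsor and ethics committee approval that 9.4 requires. There are no extra patients or visits, the 9-18 stays the same, and the related events that 4.8 counts do not change.
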